1. PROTECTION AGAINST RISK

All potential subjects will be screened for TMS and MRI risk factors prior to study enrollment. If the potential subject cannot rule out the possibility of pregnancy, a pregnancy test will be conducted prior to study enrollment. All enrolled subjects will again be screened just before undergoing MRI. These screening procedures should exclude subjects with foreseeable risks. All subjects will be monitored continuously by research investigators during MRI sessions. Subjects will be able to communicate with research investigators throughout all experimental sessions, including during MRI scans via a 2-way microphone. All subjects will wear earplugs during MRI and TMS. Earplugs will reduce the transmission of noises of the TMS coils and MRI scanner (e.g., buzzing, beeping) to a comfortable and safe level. If a subject experiences any discomfort that cannot be alleviated by the research investigators, the experimental session will be terminated.

VIII. POTENTIAL BENEFITS

Patient may benefit from this intervention by improving their symptoms of OCD. Patient randomized to the placebo arm will be given the option to enter an open-label phase when they will receive an additional 6-weeks of active rTMS.

IX. MONITORING AND QUALITY ASSURANCE

All study procedures will be in accordance with the MGH subcommittee on Human Studies. The principal investigator will oversee the collection, maintenance, and analysis of the data. Research Affairs will be contacted immediately in the case of unexpected adverse events.

A Data and Safety Monitoring Board will review the progress of the study annually, discuss any safety concerns that arise, and make recommendations to improve safety procedures if indicated. No member of the DSMB is otherwise involved with the study. Board members will consist of [name]., Assistant Professor of Radiology, Harvard Medical School; [name], President and Psychiatrist in Chief, McLean Hospital; and [name]., Associate Professor of Psychology, Tufts University. [name] was chosen for his expertise in statistical methods of neuroimaging analysis, and because, through his work as a biostatistician at the MGH and MIT General Clinical Research Centers, he has extensive experience in issues related to safe and ethical practices in biomedical research with human subjects. [name] was chosen for the DSMB because he has conducted extensive research on neuroimaging,

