Aim 3: To identify biomarkers and predictors of treatment response:

Hypothesis 3.1: We hypothesize that pathological hyperconnectivity between the pre-SMA, the Orbito-Frontal Cortex (OFC) and dorsal Anterior Cingulate Cortex (dACC) will correlate with OCD symptom severity in the pre-TMS scans.

Hypothesis 3.2: We hypothesize that (a) pathological hyperconnectivity between the pre-SMA the Orbito-Frontal Cortex (OFC) and dorsal Anterior Cingulate Cortex (dACC) and (b) early reduction of this pattern after week 1 of TMS will predict positive clinical outcomes after TMS.

III. SUBJECT SELECTION

There will be two different groups of patients with OCD in this study: one will receive active stimulation and one sham stimulation (i.e. placebo). We will recruit as many patients as are needed in order to obtain 20 completers per group (i.e. 40 patients in total). We expect an early termination rate of 30%, and we will anticipate the need to recruit and consent a total of 58 patients overall.

Inclusion Criteria:

- 1) 18-65 years of age.
- 2) Proficient in English.
- 3) A diagnosis of primary OCD (as determined by SCID).
- 4) Yale-Brown Obsessive Compulsive Scale total score ≥ 16 .
- 5) Normal (or corrected) vision.
- 6) Stable OCD medication regimen or OCD medication free for \geq 12 weeks prior to study.

7) Able to give informed consent.

Exclusion Criteria:

- 1) Current or history of neurologic or psychiatric disease (e.g., mental retardation, dementia, brain damage, or other cognitive impairment) that would interfere with ability to engage in TMS
- 2) Psychopathology not appropriate for the treatment (e.g., manic episode or psychosis)
- 3) Substance abuse or dependence that is current or within the last six months or use of an illicit drug that is not prescribed, as indicated by a urine drug screen and/or clinical inference.
- 4) Use of anticonvulsants within 2 weeks prior to study (to be ruled out by a urine drug screen.
- 5) Use of Tricyclic Antidepressants (e.g. Clomipramine).
- 6) Use of psychotropic medication is allowed (except for the limitations specified on use of OCD regimens, anticonvulsants, and tricyclic antidepressants).
- 7) Documented resistance to 4 or more valid pharmacological trials of 2 or more different medication classes (e.g. SSRIs and TCAs).
- 8) Previous exposure to TMS.
- 9) Major/chronic medical conditions.
- 10) History of head injury resulting in prolonged loss of consciousness and/or neurological sequelae.

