- 11) Prior neurosurgical procedure.
- 12) Metal in the body **that is ferromagnetic**, metal injury to the eyes
- 13) History of seizures.
- 14) Implanted pacemaker, medication pump, vagal stimulator, deep brain stimulator, TENS unit, or ventriculo-peritoneal shunt
- 15) Pregnancy; breastfeeding or nursing; for women of childbearing a pregnancy test (to be ruled out by urine β -HCG) will be conducted prior to study.
- 16) Currently in Cognitive Behavioral Therapy (CBT).
- 17) Diagnosis of primary sleep disorder such as primary insomnia, narcolepsy, sleep apnea, shift work sleep disorder and others. Sleep disorders such as insomnia or hypersomnia that are secondary to depression or OCD are permitted.
- 18) Current clinically significant suicidality

Recruitment:

OCD patients will be recruited from the Obsessive-Compulsive Disorder Clinic at MGH, as well as elsewhere in the hospital or in its clinics. Persons inquiring to other hospital research and clinical staff about OCD research opportunities may also be included. Subjects may be recruited from persons who have listed themselves on the RSVP for Health Recruitment Registry or ResearchMatch.org as volunteers to participate in OCD research. We may also use paid advertising on the internet, television, and Boston MBTA in order to reach out to more potential subjects. Efforts will be made to attain a mix of study participants, in terms of gender and racial/ethnic representation, that is reflective of the respective populations under study. Specifically, with regard to gender, it is anticipated that half of the subjects will be male, and half will be female. Similarly, it is anticipated that minority representation in the study cohorts will be

reflective of the respective populations under study. In the event that early recruitment efforts yield under-representation of any of the above groups, active outreach will be initiated (through advertisement) in an effort to achieve the above goals.

IV. SUBJECT ENROLLMENT

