The formal recruitment will take place at the first study visit to MGH. Necessary data will be gathered for the subject identification and remuneration, including date of birth, gender, years of education, address, telephone number, and social security number. Informed consent will be obtained by doctoral level licensed clinician study-staff or study staff that are doctoral candidates under the supervision of doctoral-level licensed clinicians prior to participation in the study using the e-consent module in REDCapTM and IRB-approved consent form. If the participant agrees to participate, the consent form will be signed electronically by the research participant and the individual obtaining consent. Each participant will be emailed a copy of the signed and dated consent form.

V. STUDY PROCEDURES

This study will have 2 phases: phase 1 will be a randomized, double-blinded, placebo-control trial, and phase 2 will be an open-label trial in which all patients who did not remit after completion of phase I (regardless of treatment group), will be invited to receive an additional 6 weeks of real TMS. Remitters will be defined as those subjects who have a week six Y-BOCS score of 12 or less.

1. Subjects Assessment

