As of July 8th, 2020, a majority of the clinical assessment procedures will take place virtually using Healthcare Secure ZoomTM, including the SCID-I, Y-BOCS, EHI, HAM-D, CGI, and CBF. Likewise, the following self-report instruments will be administered remotely via REDCapTM: the demographics form, OCIR, ASI, OBQ, PHQ-9, CGI – Patient Version, and covid-19 impact scale. Additionally, subjects will be screened for covid-19 symptoms before attending in-person clinical study visits (baseline, week 6, and 3-month follow-up for phases 1 and 2) by completing a covid-19 symptom attestation form via REDCapTM. Administration of the ROCF, WCST, Stroop, Goal-Oriented versus Habit-Driven Behaviors Task, BDI, BAI, STAI, and urine drug screen, however, will take place **in-person** at the MGH-main campus (Simches).

Clinical Global Impressions (CGI) scale

This global rating scale, which ranges from 1 (very much improved) to 7 (very much worse) (Rush et al, 2008), is commonly used in pharmacotherapy trials. Subjects and will complete a CGI for OCD symptoms (CGI-OCD) and for overall symptoms (CGI-global) at each assessment, captured in the CGI-Patient form. The independent evaluator will complete the CGI-OCD and CGI-global at each assessment, captured in the CGI-Clinician form. Additionally, the independent evaluator will complete a CGI-Severity (CGI-S) at baseline.

Rey-Osterrieth Complex Figure Test

The Rey-Osterrieth Complex Figure Test (ROCF; Rey, 1941 and Osterrieth, 1944) evaluates visuospatial ability, executive functioning, and memory. Subjects reproduce a complicated line drawing by copy and then by memory. Participants will be asked to copy the figure with the stimulus card present (copy trial), and later to reproduce the figure from memory at two separate time points (3 min delay and 30 min delay) followed by a recognition portion. We will score *organization* (executive function) and *accuracy* (memory) using the Savage (Savage et al., 1999) and Denman (Denman, 1984) systems, respectively. The ROCF is sensitive to change (Buhlmann et al., 2006; Park et al., 2006; Kang et al., 2003; Kuelz et al., 2006).

The Wisconsin Card Sorting Task

The Wisconsin Card Sorting Test (WCST; Grant & Berg, 1981) is a measure of executive function and strategic planning, particularly with the ability of an individual to use feedback from the environment to shift individual cognitive sets and experience goal-

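### The pregnancy test is worded two ways and dated once, before the study; it is not repeated before the optional Phase 2 course of active rTMS

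*Combined protocol and SAP*

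**What the plan says.** Three parts of the combined protocol and SAP bear on this.

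- **Section III, exclusion 15.** Pregnancy is an exclusion. The text provides "for women of childbearing a pregnancy test", names urine beta-HCG as the method, and says that it "will be conducted prior to study". I read the group meant as women of childbearing potential.
- **Section VII.1, Protection Against Risk.** "If the potential subject cannot rule out the possibility of pregnancy, a pregnancy test will be conducted prior to study enrollment". The same paragraph says that enrolled subjects are screened again just before MRI. It does not say what that screen contains.
- **Section V and V.2.2, Phase 2.** "This study will have 2 phases", and "all patients who did not remit after completion of phase I (regardless of treatment group), will be invited to receive" six further weeks of real TMS. Section V.2.2 lists the Phase 2 procedures: MRI at the end of weeks 1 and 6, and clinical and neurophysiological assessments at weeks 2, 4 and 6. It lists no pregnancy test.

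Section V.1 names the in-person clinical visits as "baseline, week 6, and 3-month follow-up for phases 1 and 2".

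**The concern.** There are two linked issues.

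First, the triggers differ. Exclusion 15 turns on childbearing potential. Section VII.1 turns on whether the candidate can rule pregnancy out. A woman of childbearing potential who says that she is not pregnant is tested under exclusion 15, but the Section VII.1 sentence alone would not prompt a test. Staff working from that section could test fewer women than the eligibility rule requires.

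Second, both rules date the test before the study, and the protocol defines one study with two phases. Entry to Phase 2 therefore does not bring a new test. A pregnancy can begin during Phase 1 without the patient knowing, and a test can find it where a question may not. For sham-arm patients, Phase 2 is the first course of active stimulation.

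What is at stake is the application of one safety exclusion. No estimate or test of any aim depends on it.

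**Working it through.** The plan states no figure for this point, so there is none to reproduce. The check compares the texts and does some simple counting.

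**Who is tested**

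| Candidate | Exclusion 15 | Section VII.1 sentence alone |
|---|---|---|
| Childbearing potential, cannot rule out pregnancy | Test | Test |
| Childbearing potential, says she is not pregnant | Test | No test prompted |

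The rules part only in the second row. Section VII.1 says if, not only if, so testing everyone whom exclusion 15 covers meets both.

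**When, and what could supply a repeat**

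- Exclusion 15 and Section VII.1: once, before the study or enrollment.
- Section V.2.2: no test among the Phase 2 procedures.
- Section VII.1 re-screen before MRI: no test named, and tied to scans rather than to TMS sessions. The first scan listed within Phase 2 is at the end of week 1, after 1 × 5 = 5 sessions. The post-Phase 1 scan would normally come before Phase 2.
- Section V.1 visit list: can be read as giving Phase 2 a baseline visit, but attaches no pregnancy test to it.

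**Size of the untested course**

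Section V.3 sets sessions on Monday to Friday for 6 weeks: 6 × 5 = 30 sessions. Section V.2.2 gives only the 6 weeks, so this assumes that the weekday schedule carries over.

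**Age of the test at the first Phase 2 session**

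- Minimum: the test precedes the 6-week Phase 1 course, so at least 6 weeks.
- Both MRI windows in full (Section V.2.1, up to 2 weeks before the first session and up to 2 weeks after the last): 2 + 6 + 2 = 10 weeks. This assumes that the test is done at the start of the first window and that Phase 2 begins at the end of the second.

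Ten weeks is a scenario and not a ceiling. The start of Phase 2 is not dated, and the test is dated only as before the study.

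**Number of repeat tests**

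Section III targets 20 completers per group, 40 in all, and expects half of subjects to be female: 0.5 × 40 = 20. This counts every woman as of childbearing potential and eligible for Phase 2. Remitters are not invited, which lowers it; the half is an expectation, so 20 is not a cap.

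**The case against.** The strongest reply is that little is broken. Several parts of it stand.

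- **The rules are compatible.** A reader might infer that the two sections conflict. The documents do not support that. Section VII.1 sets a minimum, nothing in it releases anyone from exclusion 15, and being unable to rule out pregnancy can be read as another way of describing childbearing potential. What remains is a difference in wording.
- **Re-screening exists.** The pre-MRI screen may well ask about pregnancy, and the post-Phase 1 scan falls within 2 weeks after the last session. This narrows the gap, but no test is written. Under the Section VII.1 trigger, a test would follow only where the patient is unsure.
- **The in-person procedure list proves little.** Section V.1 says that "BDI, BAI, STAI, and urine drug screen, however, will take place" in person and does not mention beta-HCG. That list also omits the entry test that exclusion 15 requires, so I place no weight on its silence.
- **Phase 1 has no repeat either, and no retest interval is given.** True. Phase 2 entry is singled out because a fresh offer of active treatment is made there, next to an in-person visit.
- **Consent pages are not in the text reviewed.** Pregnancy instructions or retesting could appear there.

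Two further inferences should be resisted. One is that the Section III exclusions lapse at Phase 2; nothing says so, and the point concerns only the test. The other is that the test may be far older than 10 weeks because Phase 2 waits for the 3-month visit. No text says that it waits: remission is judged on the week 6 Y-BOCS, and Section V.2.2 places Phase 2 after the double-blinded phase.

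**Conclusion.** The point holds as a low-priority safety improvement. The two statements of who is tested should match, although they can already be reconciled by following exclusion 15. As written, the plan gives 30 further active sessions with no repeat of the test for a condition that it excludes, and the only written test is then at least 6 weeks old, or about 10 weeks in the scenario shown.

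This rests on the weekday schedule applying to Phase 2 and on no repeat being specified in pages outside the text reviewed. The documents do not give the numbers of women of childbearing potential, of Phase 2 entrants or of pregnancies, and I assume no rate. Nothing here supports a claim of actual harm, and no aim analysis or primary result changes.

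**What to change.** 1. In Section VII.1, use the rule of exclusion 15: a urine beta-HCG for every woman of childbearing potential before enrollment.
2. In Section V.2.2, add that the urine beta-HCG is repeated for these women before the first Phase 2 session, at the in-person Phase 1 week 6 visit or at a Phase 2 baseline visit if there is one.

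The cost is two sentences, a little staff time and roughly 20 repeat urine tests on the assumptions above. If staff now follow the Section VII.1 trigger, aligning it also adds some enrollment tests, among about 0.5 × 58 = 29 women consented, but exclusion 15 already requires those. A patient who tests positive would not be offered Phase 2.

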Nevertheless, the literature on TMS for OCD remains noisy and the clinical outcomes, while promising, need improvement. An important source for this variability is the lack of individualized methods to identify and target the appropriate cortical nodes for stimulation. Our study will address this by using individual fMRI maps to identify the target and neuronavigation technology to precisely and consistently inhibit it with TMS. Another critical variable driving these inconsistencies in the field is the lack of mechanistic understanding of the effects of TMS in OCD. A priori hypotheses about disease mechanisms have driven the choices of targets of stimulations in the published clinical trials (based on a fairly robust understanding of the circuitry involved in the pathophysiology of OCD), but most studies limited themselves to measuring clinical outcomes. While this pragmatic approach is valuable, it leaves too many open questions and requires too many assumptions. Our study will innovate by proposing a translational systems neuroscience approach to understanding not only the safety and efficacy of TMS in patients with OCD, but also the physiological and anatomical changes driving (or resisting) response and remission.

II. Specific Aims

In this proposal we will apply functional neuroimaging-guided inhibitory rTMS to the pre-SMA in patients with OCD, integrating neuroimaging, behavioral and clinical research tools in a randomized controlled clinical trial. We will assess the safety and efficacy of this novel individualized strategy, study the mechanism of action at the circuit-level, and identify biomarkers and predictors of response.

Aim 1: To assess the efficacy of fMRI-guided 1HZ rTMS over the pre-SMA:

We hypothesize that patients randomized to 6 weeks of daily 1Hz rTMS will have a greater reduction in OCD symptom severity than patients randomized to identical placebo stimulation.

Aim 2: To identify the mechanisms of action of TMS at the circuit-level:

Hypothesis 2.1: We hypothesize that decreased connectivity between the pre-SMA, the Orbito-Frontal Cortex (OFC) and dorsal Anterior Cingulate Cortex (dACC) will correlate with clinical improvement.

Hypothesis 2.2: We hypothesize that TMS would improve fear extinction retention from pre- to post-treatment, and increase functional activation of the fear extinction network during extinction recall. The extinction network includes the ventromedial prefrontal cortex (vmPFC), dACC, and hippocampus.

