All candidates for this project will undergo a comprehensive clinical evaluation including a clinical interview to establish relevant psychiatric, medical and neurological history and a structured clinical interview (Structured Clinical Interview for DSM-IV Axis I Disorders; SCID-I) to confirm psychiatric diagnoses, the Edinburgh Handedness Inventory – Short Form (EHI) to establish handedness, the Beck Depression Inventory (BDI), HAM-D, and PHQ-9 to quantify depressive symptoms, the Beck Anxiety Inventory (BAI) to quantify general anxiety symptoms, the Speilberger State Trait Anxiety Inventory (STAI) to quantify trait vs. state aspects of anxiety, the Anxiety Sensitivity Index (ASI) to quantify anxiety sensitivity, and a covid-19 impact scale to assess the effect of the coronavirus pandemic in the past week. The Yale Brown Obsessive-Compulsive Scale (YBOCS), Obsessive-Compulsive Beliefs Questionnaire-44 (OBQ), the Compulsive Behaviors Form (CBF), and Obsessive-Compulsive Inventory (OCI-R) will be used to measure OCD symptoms and severity. The Clinical Global Impressions (CGI) rating scale will be used as an additional measurement of clinical change from baseline (see detailed description below). In addition, the Rey-Osterrieth Complex Figure Test and the Stroop and Wisconsin Card Sorting tasks will be conducted to assess relevant aspects of executive function and selective attention (see detailed description below). The initial evaluation of all subjects will be audio recorded for interrater reliability, and therapist supervision purposes. The digital recordings will contain participant ID numbers but not names or other identifying information. Digital recordings will be rated and simultaneously entered in the REDCap data management system for

analysis. The digital recordings will be kept by the research team in a password-protected file and destroyed after completion of the study. When possible, assessments will be used from previous studies in the OCD program (to which participants will consent).

After the initial thorough baseline assessment, patients will be assessed longitudinally through the course of the study at weeks 2, 4, 6 and 3 months after the last TMS session. These assessments will be shorter and will include the following measures: YBOCS, OBQ, OCI-R, BDI, HAM-D, PHQ-9, and covid-19 impact scale. The Rey-Osterrieth Complex Figure Test and the Wisconsin Card Sorting and Stroop tasks will also be conducted at week 6.

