At this point, the treatment session can begin. We will use an inhibitory protocol of 1Hz stimulation at 110% of the motor threshold intensity and a total of 1800 pulses per session. This will have a duration of 30 min. This protocol complies with published safety guidelines (Rossi et al., 2009). Sessions will occur daily Monday through Friday over 6 weeks.

Sham TMS will use the exact same procedure with a sham coil, which is designed to induce the same nonspecific sensory effects of TMS (auditory and somatosensory activation) without inducing the neuromodulatory magnetic fields.

4. Transcranial Magnetic Stimulation neurophysiological measures

The history of TMS has been closely linked to motor neurophysiology; the first applications were indeed geared towards the study of cortical physiology in humans. Both single and paired-pulse protocols have been established to study cortical excitability and plasticity (both intracortical inhibition and facilitation). These protocols lead to robust effects in healthy controls and are used regularly in clinical practice for diagnostic applications in neurological populations (Groppa et al., 2012). Pharmacological studies have been conducted to understand the neurochemical dynamics driving these effects (Paulus et al., 2008). Like all other TMS applications, these measures are noninvasive, and their safety has been well established (Rossi et al., 2009).

OCD results from the deficits in cortical inhibition and excessive excitatory states within specific brain networks. TMS measures of excitability, inhibition and facilitation have been shown to be abnormal in patients with OCD, to reflect clinical severity and to respond to treatment (Mantovani et al., 2013). We will use the following measures to obtain neurophysiological markers of severity and response, in addition to the other neuroimaging and behavioral measures described in this protocol.

The following 5 measures will be assessed:

- Resting Motor Threshold
- Active Motor Threshold
- Cortical Silent Period
- Short-Interval Cortical Inhibition (SICI).
- Intracortical Facilitation (ICF)

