Repetitive TMS at high frequencies has the rare potential to induce a seizure even in healthy individuals (~ 8 reported cases worldwide since the invention of TMS in 1985), but the risk for seizure can be effectively managed by using appropriate subject selection criteria and by keeping the TMS parameters within the safety parameters of the international safety consensus (Rossi et al., 2009). In addition, this study proposes the use of low-frequency rTMS, which has a cortical inhibitory effect, and single-pulse TMS for physiological assessments, which does not have carry-over cumulative effects. To protect subjects from the risk of a seizure, this study strictly adheres to the international safety consensus and will exclude subjects at increased risk for seizures (Rossi et al., 2009). In the unlikely event that a suspected seizure would occur, the seizure stops as soon as TMS is stopped, and the TMS clinical service safety plan is activated, including transfer of the subject with ambulance to MGH ER for a medical and neurological evaluation. No one has ever developed epilepsy as a consequence of TMS. There are no known or foreseeable long-term risks associated with TMS. TMS is not uncomfortable but the subject may feel twitching of the scalp muscles during stimulation. It is possible that the subject may feel headache after the TMS measurement that is caused by keeping the head in the same position for a lengthy period of time and/or by stimulation of the scalp muscles and nerves by the TMS pulses. The headache, if present, is typically mild, disappears soon and, if needed, can be treated by mild over-the-counter analgesics that are available to study participants.

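### Safety is a stated objective, but the plan schedules no systematic adverse-event collection and no safety summary by arm, and leaves unclear whether listed risks must be reported

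*Combined protocol and SAP*

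**What the plan says.** The lead-in to section II (Specific Aims) states: "We will assess the safety and efficacy of this novel individualized strategy". None of Aims 1 to 3 that follow is a safety aim.

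Section V.1 (Subjects Assessment) has patients "assessed longitudinally through the course of the study at weeks 2, 4, 6 and 3 months after the last TMS session". It gives the content of those visits as: "These assessments will be shorter and will include the following measures: YBOCS, OBQ, OCI-R, BDI, HAM-D, PHQ-9, and covid-19 impact scale". The CGI paragraph in the same section adds patient and evaluator ratings at each assessment. Some cognitive tests are repeated at week 6.

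Section V.3 (Transcranial Magnetic Stimulation) describes each treatment as "1Hz stimulation at 110% of the motor threshold intensity and a total of 1800 pulses per session" and adds: "Sessions will occur daily Monday through Friday over 6 weeks". Section V.2.2 offers non-remitters a second six-week course, this time open-label and active.

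Section VII (Risks and Discomforts) opens its account of stimulation risks with "Repetitive TMS at high frequencies has the rare potential to induce a seizure even in healthy individuals". It then says that this trial uses low-frequency stimulation, and it describes scalp twitching and headache. It sets out a clinical response to a suspected seizure.

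Section IX (Monitoring and Quality Assurance) contains the one explicit reporting rule: "Research Affairs will be contacted immediately in the case of unexpected adverse events". It also sets up a DSMB that reviews participant safety once a year, and sooner if a safety matter comes up.

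**The concern.** A trial that sets out to assess safety needs three things: a definition of what is counted, a fixed occasion on which everyone is asked, and a planned summary by arm. The plan appears to have none of them. Events noticed only when a patient volunteers them, or when staff happen to write them down, do not give a rate that can be compared between active and sham.

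Tolerability is the more practical loss. The plan expects 30% of patients to stop early, and section VII.1 allows a session to be ended for discomfort that cannot be relieved. No reason for either is to be recorded. If active stimulation were less well tolerated than sham, the data would not show it. Session-level events that go unrecorded cannot be reliably recovered later.

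The reporting rule adds a second difficulty. It depends on an undefined word, and the protocol itself lists several risks that a reader could therefore regard as expected.

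**Working it through.** **1. The plan's own figures.** The documents give no safety figure, so the only ones to reproduce concern efficacy and recruitment.
- Power with 20 per group, d = 1.06 and two-sided alpha 0.05 (section VI, Power for the Primary Aim). Normal approximation: Φ(1.06 × √(20/2) − 1.96) = Φ(1.39) = 91.8%. Two-sample t-test (noncentral t): 90.4%. The plan states 90%, which reproduces.
- Recruitment (section III): 40 / (1 − 0.30) = 57.1, rounded up to 58. This also reproduces. The expected loss is 58 − 40 = 18 patients. Some of these may leave before randomisation, because 58 counts patients consented.

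**2. Tracing what a safety answer needs.**
- *Objective:* present (section II lead-in).
- *Event definition:* absent. Neither serious nor unexpected is defined.
- *Collection at visits:* absent. The follow-up battery in section V.1 consists of OCD and depression scales and a covid-19 impact scale. CGI and cognitive tests are added, but no side-effect form is named. Section VII mentions in passing that patients may find it uncomfortable to talk about side effects, but this schedules no query.
- *Collection at sessions:* absent. Sections V.2 and V.3 cover threshold, targeting, pulses and timing, with no event query.
- *Reasons for stopping a session or leaving the study:* not recorded as data anywhere.
- *Analysis:* absent. Section VI covers Y-BOCS, neurophysiology and MRI. It has no safety population, outcome or table.
- *Oversight:* a DSMB exists, but the contents of its data package are not stated.
- *Reporting:* one rule, for unexpected events. The seizure response in section VII names no reporting step.

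**3. Occasions already available.** Five sessions a week for six weeks is 5 × 6 = 30 sessions per course. A patient who is active in both phases would have 60. Phase 1 also has four follow-up assessments. No new visit is needed to collect events.

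**4. What collection could show.** With zero events of a given kind in n patients, the one-sided 95% upper bound on the rate is 1 − 0.05^(1/n).
- n = 20 active completers: 1 − 0.05^(1/20) = 13.9%.
- n = 29 active, assuming all 58 are randomised equally: 1 − 0.05^(1/29) = 9.8%.

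**5. Power for a common event.** The documents give no headache rates, so the rates below are assumptions. Two-sided Fisher exact test at 0.05:

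| Sham vs active (assumed) | 20 per arm | 29 per arm |
|---|---|---|
| 10% vs 30% | 24% | 35% |
| 10% vs 40% | 49% | 68% |

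Under these assumptions a formal test would be weak, so a descriptive table is the right level of ambition.

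**The case against.** The strongest reply is that safety oversight does exist. The DSMB reviews participant safety every year and can be consulted earlier on any safety issue, not only unexpected events. All procedures fall under the institution's human-studies committee. A suspected seizure activates a clinical service safety plan that is not among the documents and may contain a reporting step. An operations manual may do the same for other events. CGI ratings by patient and evaluator at each assessment, with repeated depression scales, could show general deterioration by arm. At this sample size, a between-arm safety test would be weak anyway.

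Much of this stands, and it rules out three stronger readings.
- A reader might infer that a seizure is excluded from reporting because it is a listed risk. The documents do not support that. Section VII ties seizure to high-frequency stimulation and calls it unlikely in this trial, and *unexpected* is undefined. A seizure at 1 Hz could well be treated as unexpected. The text is unclear; it does not exclude seizure.
- A reader might infer that nothing but unexpected events can be escalated. The DSMB route contradicts this. The limit applies only to contact with Research Affairs.
- A reader might infer that no safety information by arm could exist. CGI worsening could be tabulated, and a seizure leading to ambulance transfer would hardly go unnoticed.

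The reply does not fill the gap itself. A scale of overall change does not identify headache, scalp pain or a session cut short. A board can review only what it is given, and the plan does not say what that is. Compliance with institutional policy would not create a summary by arm. Low power argues against a formal test, not against recording events.

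**Conclusion.** The point holds as a gap between a stated objective and the planned data. Safety is to be assessed, yet no systematic adverse-event or tolerability collection is scheduled and no summary by arm is planned. Followed as written, the plan gives no event or tolerability rate for either arm. The 18 or so expected losses could not be divided into those caused by discomfort and the rest. Separately, it is unclear whether listed risks, seizure among them, must go to Research Affairs.

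The primary efficacy analysis is unaffected. The information lost is modest but real: at best, bounds of about 10% to 14% on events not seen in the active arm, and descriptive rates for common ones. The 10% end assumes 29 patients randomised to active treatment. The judgement rests on the public text; a separate manual could already supply part of what is missing. This should be corrected, but it does not call the trial's validity into question.

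**What to change.** - **Collect.** At each existing treatment session and assessment visit, have the operator or assessor complete a short standard form. It should record all adverse events, expected or not, with severity, and any early end to a session or to participation, with the reason. REDCap is already in use.
- **Summarise.** Add to section VI a descriptive table by randomised arm for all patients who start stimulation, with Phase 2 shown separately. No hypothesis test is needed. Supply the table to the DSMB for its annual review.
- **Report.** Define serious and unexpected in section IX, and state that the reporting rule covers serious events and seizures whether or not they are listed as risks.

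The protocol is dated August 2020 and refers to participants randomised before February 2018, so some patients have probably already been treated. The table should say from what date the form was in use and should keep earlier, unsystematic records apart.

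The cost is a small amount of data entry per session, one table and a short amendment to section IX. No visit is added, and no treatment or clinical rule changes.
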